12.4 Participant and data confidentiality

All parties will ensure protection of subject personal data and will not include subject names on any Sponsor forms, reports, publications, or in any other disclosures, except where required by law. In case of data transfer, the Sponsor will maintain high standards of confidentiality and protection of subject personal data.

The Sponsor and designees affirm and uphold the principle of the subject's right to protection against invasion of privacy. Throughout this study, a subject's source data will only be linked to the Sponsor's clinical study database or documentation via a unique identification number. As permitted by all applicable laws and regulations, limited subject attributes, such as sex, age, or date of birth, and subject initials may be used to verify the subject and accuracy of the subject's unique identification number.

To comply with ICH Guidelines for GCP and to verify compliance with this protocol, the Sponsor requires the Investigator to permit its monitor or designee's monitor, representatives from any regulatory authority (e.g., FDA), the Sponsor's designated auditors, and the appropriate IRBs and IECs to review the subject's original medical records (source data or documents), including, but not limited to, laboratory test result reports, ECG reports, admission and discharge summaries for hospital admissions occurring during a subject's study participation, and autopsy reports. Access to a subject's original medical records requires the specific authorization of the subject as part of the informed consent process.

Copies of any subject source documents that are provided to the Sponsor must have certain personally identifiable information removed (i.e., subject name, address, and other identifier fields not collected on the subject's source documents).

13 Data handling and record keeping

13.1 Study records retention

To enable evaluations and/or audits from regulatory authorities or the Sponsor, the Investigator agrees to keep records, including the identity of all participating subjects (sufficient information to link records, e.g., CRFs and hospital records), all original signed Informed Consent Forms, copies of all CRFs, SAE forms, source documents, detailed records of drug disposition, and adequate documentation of relevant correspondence (e.g., letters,

meeting minutes, telephone calls reports) for a duration of five (5) years.

The records will be retained by the Investigator according to the International Conference on Harmonization (ICH), local regulations, or as specified in the Clinical Study Agreement.

If the Investigator or investigational Site becomes unable for any reason to continue to retain study records for the required period (e.g., retirement, relocation), the Sponsor will be prospectively notified. The study records must be transferred to a designee; research site owner, as accepted by the Sponsor, such as another Investigator, another institution, or to the Sponsor. The Investigator must obtain Sponsor's written permission before disposing of any records, even if retention requirements have been met.

13.2 Protocol deviations

The Investigator should not deviate from the protocol, except where necessary to eliminate an immediate hazard to study subjects. The site should document all protocol deviations in the subject's source documents. In the event of a significant deviation, the site will notify the Sponsor or its designee (and IRB or IEC, as required). Significant deviations include, but are not limited to, those that involve fraud or misconduct, increase the health risk to the subject, or confound interpretation of primary study assessments. Deviations from the inclusion/exclusion criteria will not be permitted unless written approval by the Sponsor has been obtained. Should other unexpected circumstances arise that will require deviation from protocol-specified procedures, the Investigator will contact the Sponsor or designee at the below mentioned address in order to determine the appropriate course of action.

Site will be responsible for proper maintaining and filing of all Protocol Deviation related documentation in the site files.

Protocol Compliance review:

- Verify that the Investigator and Investigational Site personnel are adhering to the IRB/IEC approved Protocol and all amendments. In addition to the Protocol, the Monitoring Plan may include (or reference) verification strategies which define a percentage of data points to be reviewed or other methodologies for verification of Investigational Site compliance. The Monitoring Plan should be followed regarding verification and study specific problem escalation, and Protocol compliance is often reviewed by checking adherence to the correct Protocol-defined procedures, assessments, and sampling requirements (if applicable).
- Verify that the Investigator is enrolling only eligible Study participants and all entry criteria are satisfied for each Study participant verified, as per the current approved Protocol. Documentation and verification of participant status in the study.
- Verify that no prohibited medications or changes in dose for indication-related medications are being used without prior approval from Medical Monitor or Sponsor Designee.
- Address any protocol deviations with site personnel during the IMV and identify ways to prevent the recurrence of similar issues e.g. training the site team on that particular issue.

16.1 Schedule of events

Visit Number	Visit 1	Visit 2	Visit 3	Visit 4
Visit Day	Day 0	Day 2	Day 7	Day 14
Informed Consent	X			
Eligibility Criteria	X			
Subject Demographics	X			
Medical History	X	X	X	X
Physical Examination	X	X	X	X
Combing		X	X (if treatment needed)	
Investigational Product Dispensation	X		X (if necessary)	
Vital Signs	X	X	X	X
Urine Pregnancy Test	X	X	X	X
Head Lice Visual Assessment	X	X	X	X
Local Skin/Scalp Irritation Assessment	X	X	X	X
Ocular Irritation Assessment	X	X	X	X
Concomitant and Prohibited Medication Review	X	X	X	X
Adverse Events Assessment	X	X	X	X

16.2 Subject household information

SUBJECT DIARY

Protocol Number: ALLI010-0021

Study Title: A Study to Evaluate the Safety and Efficacy of Alliance Pharmaceutical Product
Vamousse Spray 'n' Go in Subjects Infested with Pediculosis Capitis.

SUBJECT NUMBER:						SUBJECT INITIALS:		
BASELINE VISIT DATE:								
D	D	M	M	M	Y	Y	Y	Y

To be completed by the study team member & cover page to remain at the site

SUBJECT HOUSEHOLD INFORMATION

Study Visit

Visit 1

HOUSEHOLD MEMBERS TREATMENT INFORMATION

Number of Infested Household Members

Number of Non-Infested Household Members

Total Number of Household Members

Infested Household Member # 1 Standard of Care Treatment	Yes	No	Circle (Yes) or (No)
Infested Household Member # 2 Standard of Care Treatment	Yes	No	
Infested Household Member # 3 Standard of Care Treatment	Yes	No	
Infested Household Member # 4 Standard of Care Treatment	Yes	No	
Infested Household Member # 5 Standard of Care Treatment	Yes	No	
Infested Household Member # 6 Standard of Care Treatment	Yes	No	
Infested Household Member # 7 Standard of Care Treatment	Yes	No	

16.3 Subject home instructions

SUBJECT NUMBER:							SUBJECT INITIALS:	
VISIT DATE:								
	D	D	M	M	M	Y	Y	Y

Subjects Home Instructions

Activity	Application of study drug – Day 0						Complete																						
To be completed by Study staff	
 Was product Applied Onsite? 						Yes	No																					
Date of Application																													

 
 	
 
 D	D	M	M	M	Y	Y	Y	Y		
 
																				D	D	M	M	M	Y	Y	Y	Y	
D	D	M	M	M	Y	Y	Y	Y																					
Time of Application																													

 
 	
 
 H	H	M	M							
 
																				H	H	M	M						
H	H	M	M																										
To be completed by subject/or caregiver	
 Was the hair wash, or rinse 8-hours post-treatment? 						Yes	No																					
Date to Shampoo Hair																													

 
 	
 
 D	D	M	M	M	Y	Y	Y	Y		
 
																				D	D	M	M	M	Y	Y	Y	Y	
D	D	M	M	M	Y	Y	Y	Y																					
Time to Shampoo Hair																													

 
 	
 
 H	H	M	M							
 
																				H	H	M	M						
H	H	M	M																										
LAUNDRY DISINFECTION:	
 Was all recently worn clothing, hats, used bedding & towels washed at home? 						Yes	No																					

Subject and/or Caregiver (Initials): _____

Date: _____

Completed & Reviewed By (Initials): _____

Date: _____

16.4 Subject self-assessment

SUBJECT SELF ASSESSMENT

SITE PERSONELL TO COMPLETE:

SUBJECT NUMBER:							SUBJECT INITIALS:		
VISIT DATE:									
	D	D	M	M	M	Y	Y	Y	Y

Visit Number	Visit 1 [Baseline]	Visit 2 [Follow Up]	Visit 3 [Follow Up]	Visit 4 [Final Visit]
Visit Day	Day 0	Day 2	Day 7	Day 14

TO BE COMPLETED BY SUBJECT AND/OR CAREGIVER:

This assessment is aimed to rate the itching and stinging/burning sensations you may have experienced after the application of the study product. Please rate the experience in the tables below.

ITCHING

(Intense, distracting irritation or tickling sensation in the last 24 hours)

Score	Grade	Definition	Check one
0	None	The scalp does not itch.	
1	Mild	Occasional episodes of itching, not bothersome.	
2	Moderate	Frequent, several times a day, bothersome.	
3	Severe	Nearly constant, frequent, very bothersome.	

STINGING/BURNING

(Sensation of the skin is painfully hot or noticeable tingling sensation in the last 24 hours)

Score	Grade	Definition	Check one
0	None	Absent	
1	Mild	Slight, barely present	
2	Moderate	Distinct presence	
3	Severe	Marked, intense	

Subject and/or Caregiver (Initials): _____ Date _____

Completed & Reviewed By (Initials): _____ Date: _____

ALLI010-0021

Version 3.0

27 July 2022

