Study Objectives	
The primary objective of the study will explore whether treatment with Vamousse Spray 'n' Go is more effective in killing lice & eggs compared to a permethrin-based control product.
 
The secondary objective of the study is to demonstrate the safety and local tolerability of Vamousse Spray 'n' Go in children 2yo+.

Study Endpoints	
The primary efficacy endpoint is the proportion of subjects who are lice free (defined as no live lice, adults or nymphs) 14 days after treatment.
 
The secondary efficacy endpoint is the number and percentage of all subjects who are lice-free at Day 2.

Number of Subjects and Site	The planned overall sample size for this Open-Label Clinical Trial is approximately 58 subjects to be enrolled at clinical research center in the United States, specifically Miami, FL. The subjects will be evenly divided between the Spray 'N' Go treatment group and the permethrin control group (29 subjects in each).
Eligibility Criteria	Subjects who satisfy ALL the inclusion criteria and have NONE of the exclusion criteria may be enrolled in the study.

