4.2.3 Secondary Endpoints

- Assessment of infestations detected: number of live adult and nymph forms at the 7-day visit confirmed by investigator inspection during detection combing.
- Proportion of subjects requiring re-treatment at 7 days.
- Proportion lice free at day 2 (i.e., 24 hours after first treatment)
- Volume of product used in relation to hair type (Volume will be weighted pre and post and weight will be recorded on the product log. Hair type will be recorded as fine, medium or coarse on source document.)
- Safety of the product – as determined by reported adverse events during the study and recalled at the end of the treatment period.
- Cosmetic acceptability of the product in daily use as determined by consumer assessment questionnaire at the 14-day visit.
- The mean change between day 14 and baseline in the counts of live lice (i.e., total of live adult lice and nymphs) in each study group (i.e., treatment and control).

5. Study Enrollment and Withdrawal

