7.1.1. Study specific procedures

In addition to the regular standard of clinical care, the following study specific procedures will be included as part of the study.

- Past medical history of and previous treatment of head lice must be recorded irrespective of the term it was given. Corresponding condition shall be captured in the subject's Medical History.
- Visual Assessment of Head Lice:
Subjects and their household members will be thoroughly assessed for the presence or absence of live head lice, including adult lice, nymphs, and nits. Results will be recorded on Source Document.
- Skin/Scalp Irritation Assessment:
Subjects will be assessed for skin and scalp pruritus, erythema, excoriation, and pyoderma. Results will be recorded on the Source Document.
- Ocular Irritation:
Subjects will be assessed for eye irritation, conjunctivitis, and ocular hyperemia. Results will be recorded on the Source Document.
- Subject Household Instructions:
Administration of a checklist for rinse/ shampoo time and date; and daily laundry and disinfection measures will be collected at all follow-up visits.
- Subject Assessments:
Administration of questionnaire for subject-reported outcomes. The site will complete a Subject Self-Assessment Worksheet to record the grading of Itching and Stinging/Burning sensations. Analysis of tolerability will be based on a 7 point scoring scale of Stinging/Burning and Itching sensations collected during Subject Self-Assessment at all follow-up visits.

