7.3.2 Follow up

Follow-up Visit (Day 2) Visit 2 (+24hrs.)

- Medical History, Vital Signs, Physical Examination, Head Lice Visual Assessment, Local Skin/Scalp Irritation, Assessment, Ocular Irritation Assessment. Record results on Source Document.
- Record adverse events as reported by participant or observed by investigator.
- Record subject's adherence to homecare instructions.
- Perform assessment for living head lice on subject for visual confirmation of infestation.
- Record subject's adherence to homecare instructions.
- Inform each subject when to come back for their visit (Day 7) Visit 3 ± 1 days

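### The tolerability form's 24-hour recall misses any Day 7 spray re-treatment, its coverage of the Day 0 application depends on an unresolved Day 2 timing, and its 7-point score is undefined

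*Combined protocol and SAP*

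**What the plan says.** The synopsis gives as the secondary objective to "demonstrate the safety and local tolerability of Vamousse Spray 'n' Go in children 2yo" and older. It bases the tolerability analysis on stinging/burning and itching scores at all follow-up visits, compared between the groups. It states no scale length and no rule for summing. Section 7.1.1 adds: "Analysis of tolerability will be based on a 7 point scoring scale of Stinging/Burning and Itching sensations". Section 10.4.3 names only adverse events as safety variables.

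The form in 16.4 introduces itself as a rating of "sensations you may have experienced after the application of the study product". The item definitions are narrower. Itching is "Intense, distracting irritation or tickling sensation in the last 24 hours" and stinging/burning is "Sensation of the skin is painfully hot or noticeable tingling sensation in the last 24 hours". Each item has four grades, 0 to 3. The form prints columns for Day 0 (labelled baseline), Day 2, Day 7 and Day 14, but does not say whether the Day 0 column is filled in before or after application. The schedule of events (16.1) does not list the form.

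The spray stays in for at least 8 hours and is washed off at home. Staff rinse off the control after 10 minutes (4.1, 6.1.5). A second application is given at the Day 7 visit if live lice are present (7.3.3).

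The timing of Day 2 is given in two ways. Section 4.2.3 has "Proportion lice free at day 2 (i.e., 24 hours after first treatment", whereas 7.3.2 has "Follow-up Visit (Day 2) Visit 2 (+24hrs" and 6.1.7 makes the treatment day Day 0.

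**The concern.** The form states one aim and its items measure another. A question about the past 24 hours, asked days after the product was washed off, records what is left over. It does not record what the subject felt while the product was on the scalp. The two products also have very different contact times, so a fixed look-back from the visit can reach one exposure and not the other.

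This matters because local tolerability in young children is a stated objective, and this form is the only structured score of stinging and burning. Low scores could be read as good tolerability when the exposure period was not asked about. If the two items are also summed, itch that persisting lice can cause is mixed with stinging from the product.

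**Working it through.** **Inputs.** Recall is 24 h for both items (16.4). Spray exposure is 8 h, the stated minimum (6.1.5). Control exposure is 10 min, or 10/60 = 0.17 h (4.1). Windows are Day 7 ± 1 (7.3.3) and Day 14 ± 2 (7.3.4), or ± 3 in the synopsis and 6.1.7. Time is counted from the start of application.

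**Formula.** For a form completed t hours after application, with exposure E and t at least 24 h, the covered exposure is max(0, E − (t − 24)).

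**First application (Day 0).**

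| Form at | Spray, E = 8 h | Control, E = 0.17 h |
|---|---|---|
| 24 h | 8 − 0 = 8 h | 0.17 h (all) |
| 26 h | 8 − 2 = 6 h | 0 |
| 28 h | 8 − 4 = 4 h | 0 |
| 32 h | 8 − 8 = 0 | 0 |
| 48 h | 0 | 0 |
| 72 h | 0 | 0 |

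The 24 h row is the reading in 4.2.3. The 48 h row is Day 2 counted from Day 0. The 72 h row applies if the 24 hours in 7.3.2 is a window added to 48 h. Control coverage is lost once t passes 24.17 h. A visit between then and 32 h therefore reaches part of the spray exposure and none of the control exposure. With longer leave-in times (my assumption), spray coverage ends at 36 h for 12 h of contact and at 48 h for 24 h. A form at 48 h covers none of it in any of these cases.

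**Second application (Day 7).** The shortest gap to the next form is the latest Day 7 visit to the earliest Day 14 visit:
- Window ± 2: (12 − 8) × 24 = 96 h, so recall begins 96 − 24 = 72 h after application.
- Window ± 3: (11 − 8) × 24 = 72 h, so recall begins 72 − 24 = 48 h after application.
- Nominal days: (14 − 7) × 24 = 168 h, so recall begins 144 h after application.

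Coverage of an 8-hour exposure is zero in each case. The Day 7 form cannot cover hours that follow at home. If completed after re-treatment, which the protocol does not settle, it could include the control's whole 10 minutes but only the on-site part of the spray exposure.

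**How many subjects.** The protocol gives no expected re-treatment rate. Section 10.5 reports a single-treatment pilot with 88% lice free just after treatment and 12% at Day 14, and relies on repeat dosing. If the share still infested at Day 7 lies between 100 − 88 = 12% and 100 − 12 = 88% (an assumption), then of 29 spray subjects between 0.12 × 29 = 3.5 and 0.88 × 29 = 25.5 would be re-treated.

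**Scale.** Each item has levels 0, 1, 2, 3, so four points. The sum of the two items runs from 0 to 6, which is exactly seven levels. The figure in 7.1.1 can thus be reproduced, but only as a sum that no section states. A total of 2 could then be moderate stinging with no itch, or moderate itch with no stinging.

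**The case against.** The strongest reply is that 4.2.3 places Day 2 at 24 hours, where the form covers the full 8 hours of spray and the control's 10 minutes. That stands. A reader might infer that both applications are missed outright. The documents do not support this for the first one, where the defect is a timing contradiction. The reply holds only for a visit at almost exactly 24 h, however, because small delays remove the control exposure first.

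The form also has a Day 0 column. If completed after application it could capture the control's contact time and the start of the spray's, but not the hours at home, and the stated analysis uses follow-up visits.

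Safety capture does not rest on this form alone. Adverse events are recorded from the first application with no 24-hour limit and are recalled at the end of treatment. Scalp irritation is assessed at every visit. This stands and limits the consequence. The scalp assessment in 7.1.1, however, lists pruritus, erythema, excoriation and pyoderma, and has no item for stinging or burning.

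The second-application gap concerns only subjects with live lice at Day 7. Section 5.5.1 (item 5) would instead terminate still-infested subjects at a revisit, which conflicts with 7.3.3. Those passages must be reconciled, and the number affected depends on the outcome.

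**Conclusion.** The point holds in a limited form. Any Day 7 spray exposure at home is missed under every stated window. For the Day 0 application, coverage ranges from all 8 hours to none depending on which Day 2 timing applies, and between just over 24 h and 32 h it differs by arm. The comparison of stinging/burning can therefore understate the sensations during contact, or measure them unequally. The 7-point score is undefined. It is not shown to be a wrong number, since a 0–6 sum would produce it.

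Two further inferences are tempting and not supported. One is that stinging would be scored near zero in both arms however irritating the product. Section 2.3.1 lists allergic skin reaction, dryness and cracking, and such effects may outlast contact. The other is that the more effective arm will look better tolerated because lice cause itch. That is plausible, but nothing in the documents shows it.

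The result rests on the wording of 16.4 as printed and on the 8-hour minimum contact time. The importance is minor to moderate. The change is worth making because it serves the secondary objective at almost no cost. The primary endpoint is unaffected.

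**What to change.** 1. In 16.4, replace the 24-hour limit with a single recall window, the worst sensation since the most recent application, on the first form after each application: Day 2 for the Day 0 application, and Day 14 for a Day 7 re-treatment. Complete the Day 7 form before any re-treatment.
2. Analyse stinging/burning and itching as two separate 0–3 scores, and correct 7.1.1 to say so.
3. Make the post-application stinging/burning score the main tolerability comparison. The Day 2 score is due from every treated subject. Summarise the Day 14 score after re-treatment separately, because that group is selected by lice status at Day 7. Report itch alongside lice status.
4. Reconcile the Day 2 timing in 4.2.3 and 7.3.2.

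A caregiver score at wash-off on the 16.3 home sheet would be a weaker remedy. Control hair is rinsed on site after 10 minutes, so time, setting and rater would differ by arm, and that sheet covers only Day 0.

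The cost is a change of form wording and a few lines of protocol text. The downside is longer recall by the subject or caregiver, about a week for a Day 7 re-treatment.
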